8.4.2 Definition of an Adverse Event

The FDA Safety Guidance, referencing 21CFR312.32(a), defines an Adverse Event as follows:

Adverse event means any untoward medical occurrence associated with the use of a drug in humans, whether or not considered drug related.

An adverse event (also referred to as an adverse experience) can be any unfavorable and unintended sign (e.g., an abnormal laboratory finding), symptom, or disease temporally associated with the use of a drug and does not imply any judgment about causality. An adverse event can arise with any use of the drug (e.g., off-label use, use in combination with another drug) and with any route of administration, formulation, or dose, including an overdose.

Adverse Events are **NOT**:

- Clinical events related to the progression of COVID-19.
- Medical or surgical procedures (e.g., surgery, endoscopy, tooth extraction, transfusion). The condition that leads to the procedure is the AE.
- Situations where an untoward medical occurrence has not occurred (e.g., hospitalization for elective surgery, social and/or convenience admissions).

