8.4.3 Evaluating and Reporting of Adverse Events

All AEs (i.e. a new event or an exacerbation of a pre-existing condition) that occur after dosing with favipiravir and after completion of baseline assessments in the SOC alone arm, must be recorded as an AE or SAE (if applicable), on the Adverse Event eCRF and SAE form, as applicable. The Investigator must follow all AEs until the AE resolves, or until the Investigator and/or the Medical Monitor determine the event is chronic or clinically stable. If an AE remains unresolved at the conclusion of the study, the Investigator and Medical Monitor will make a clinical assessment to determine whether continued follow-up of the AE is warranted. All subjects who have received at least one exposure to study therapy will be evaluated for safety of study treatment.

The Investigator should attempt to establish a diagnosis of the event based on signs, symptoms and/or other clinical information. In such cases, the diagnosis should be documented as the AE and not the individual signs/symptoms.

All AEs must be promptly documented on the Adverse Event eCRF and assessed by the Investigator. Details of the event must include the dates of onset and resolution, severity, relationship to study drug, seriousness, and whether the event caused the subject to withdraw from the study, outcome and timing with regard to administration of the study drug.

Severity: Severity should be graded and recorded as follows:

- Mild: Awareness of event but easily tolerated
- Moderate: Discomfort enough to cause interference with usual activity
- Severe: Inability to carry out usual activity, incapacitating, requires medical intervention

Relationship: The relationship of the Adverse Event to the study drug will be determined by the Principal Investigator, and assessed using the following definitions:

• **Related:** There is a distinct temporal relationship between the event onset and administration of the study drug. There is a known reaction to agent or chemical group or

predicted by known pharmacology. The event cannot be explained by subject's clinical state or other factors.

• Unrelated: Evidence exists that the AE has an etiology other than the study drug (e.g., pre-existing condition, underlying disease, intercurrent illness, or concomitant medication).

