8.4.5 Definition of Serious Adverse Events

An SAE is an AE from this study that results in any of the following outcomes:

- Death (even if caused by COVID-19 all deaths are recorded as SAEs)
- Life-threatening situation (subject is at immediate risk of death)
- Inpatient hospitalization or prolongation of existing hospitalization
- Persistent or significant disability/incapacity
- Congenital anomaly/birth defect in the offspring of a subject who received study drug

NOTE: Important medical events that may not result in death, be immediately life-threatening, or require hospitalization, may be considered an SAE when, based upon appropriate medical judgment, they may jeopardize the subject *and* may require medical or surgical intervention to prevent one of the outcomes listed in this definition.

A life-threatening AE is defined as any adverse experience that places the subject in the view of the Investigator, at immediate risk of death from the event as it occurred. This does not include an event that might have led to death, if it had occurred with greater severity.

"Inpatient hospitalization" means the subject has been formally admitted to a hospital for medical reasons, for any length of time. Presentation and care within an emergency department does not necessarily constitute an SAE. Complications that occur during hospitalization are AEs. If a complication prolongs hospitalization, it is an SAE.

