9.7 Safety Analysis

The original exact terms in the electronic data capture (EDC) system used by Investigators to identify AEs other than symptoms of COVID-19 will be fully described and coded according to the Medical Dictionary for Regulatory Activities (MedDRA). Treatment-emergent AEs will be defined as those occurring coincident with start of treatment and through Day 60. TEAEs will be summarized overall and by treatment group and by MedDRA body organ system and preferred term, severity, relatedness, and seriousness.

An overall summary of TEAEs will be presented by treatment, with subject counts and percentages of subjects with the event. This summary will include subjects with any TEAE, any treatment-related TEAE, any serious TEAE, any treatment-related serious TEAE, TEAEs leading to study infusion discontinuation, treatment-related TEAEs leading to study infusion discontinuation, TEAEs leading to death, and treatment-related TEAEs leading to death. The difference in proportions between treatment groups in each of these categories will be calculated.

Summaries of changes over time in laboratory parameters, as well as counts and percentages of laboratory parameters that are Low, Normal, and High compared to the reference ranges will be presented by treatment at each visit and time point. Shift tables will be presented for laboratory parameters with defined severity grades.

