#### 4.5.2. Adverse Events

All AEs will be coded using the MedDRA v23.0 coding system and displayed in tables and data listings using system organ class and preferred term. Missing and partial dates will be handled as described in [Section 3.10.2](#).

Treatment-emergent AEs (TEAEs) will be defined as those occurring coincident with start of treatment through Day 60.

In the favipiravir + SOC arm: Adverse event solicitation and recording will begin immediately following the first dose of favipiravir and will include only on-treatment (treatment-emergent) events. Any changes to a subject's health that occur between the signing of the informed consent and dosing will be recorded as updates to the subject's medical history.

In the SOC alone arm: Adverse event solicitation and recording will begin following the completion of all baseline assessments.

Clinical events related to the progression of COVID-19 will **not** be considered AEs.

Adverse events are summarized by subject incidence rates; therefore, in any tabulation, a subject contributes only once to the count for a given AE in both SOC and preferred term.

The number and percentage of patients with any TEAE, with any TEAE assessed by the Investigator as related to treatment, with any serious TEAE, and with any treatment-emergent serious AE (SAE) potentially related to treatment will be summarized by treatment group and overall.

All AEs occurring on-study will be listed in subject data listings.

By-subject listings also will be provided for the following: subject deaths, SAEs, and AEs leading to treatment/study discontinuation.

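### Protocol 8.4.2, 8.4.5 and 9.7 and SAP 4.5.2 give no single rule on whether serious COVID-19 progression is an adverse event, so the serious-event tables can be built in more than one way

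*Protocol*

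**What the plan says.** Five places bear on the point.

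- **Protocol 8.4.2** lists "Clinical events related to the progression of COVID-19" among the things that are not AEs. It makes no exception for death or seriousness and gives no criterion for deciding that an event is progression.
- **Protocol 8.4.3** describes what must be recorded as "All AEs (i.e. a new event or an exacerbation of a pre-existing condition", again without mentioning COVID-19.
- **Protocol 8.4.5** opens with "An SAE is an AE from this study that results in any of the following outcomes". Its first listed outcome is "Death (even if caused by COVID-19 all deaths are recorded as SAEs". The paragraph on hospitalization ends with "Complications that occur during hospitalization are AEs. If a complication prolongs hospitalization, it is an SAE".
- **Protocol 9.7** words the exclusion differently: "AEs other than symptoms of COVID-19 will be fully described and coded". Its planned summary includes serious TEAEs and ends with "TEAEs leading to death, and treatment-related TEAEs leading to death. The difference in proportions between treatment groups in each of these categories will be calculated".
- **SAP 4.5.2** repeats the 8.4.2 exclusion ("Clinical events related to the progression of COVID-19 will" not count as AEs) without the death exception. It then summarizes subjects with any serious TEAE by arm. Deaths and SAEs also appear as by-subject listings.

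The trial is open label (protocol 3), and the investigator assesses AEs and their relationship to study drug (8.4.3). No blinded adjudication is described. SAP 5 records one change from the protocol, the removal of hierarchical testing, and is silent on this matter.

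**The concern.** Every subject enters the trial hospitalized with COVID-19, so worsening of that disease is an obvious source of serious events. If an SAE must first be an AE, and progression is not an AE, a serious progression event cannot be an SAE. Other sentences in 8.4.5 nevertheless bring such events in.

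Two things are at stake. The first is the between-arm safety comparison: safety against SOC is a secondary objective (protocol 4.2), and 9.7 asks for differences in proportions for serious and fatal TEAEs. The second is reporting: under protocol 8.5 the sponsor's SUSAR assessment starts after the investigator reports an SAE, so a non-fatal event set aside as progression may not reach that review. In an open-label trial, the person who sets it aside knows the arm.

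**Working it through.** **Step 1: set the rules side by side.**

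| Event | 8.4.2 and SAP 4.5.2 | 8.4.5 | Result |
|---|---|---|---|
| COVID-19 death, site recording | Not an AE | SAE, with the disease named | 8.4.5 reads as a deliberate exception; reasonably clear |
| COVID-19 death, analysis | Not an AE; the SAP has no exception | SAE | Open whether it enters the serious-TEAE row (SAP 4.5.2) or the fatal-TEAE row (protocol 9.7) |
| Non-fatal serious progression, such as respiratory failure that lengthens the stay | Not an AE | Complication, so an AE; it lengthens the stay, so an SAE | Conflict, with no stated precedence |
| Non-serious COVID-19 symptoms | Not an AE if they reflect progression | Covered only if regarded as a complication | Wording differs again in 9.7 (symptoms rather than progression) |

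**Step 2: what can be sized.** The documents give no rate for death or serious progression, so there is no plan figure on this point to reproduce. The only document input is the planned size: about 50 subjects randomized 1:1, or 50 / 2 = 25 per arm. Every risk below is an assumption.

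*Deaths alone.* Assume COVID-19 mortality of 10-20%. Then 0.10 x 25 = 2.5 and 0.20 x 25 = 5 deaths per arm, or 10-20 percentage points of the serious-TEAE row. This is an upper bound: a subject who died may already be in the row through another serious event.

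*All three readings.* As a separate illustration, assume mutually exclusive categories per arm of 25:

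- other serious events 4-8%: 1-2 subjects;
- COVID-19 death 4-12%: 1-3 subjects;
- serious non-fatal progression 8-24%: 2-6 subjects.

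Expected subjects with a serious TEAE:

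- strict 8.4.2 and SAP 4.5.2: 1-2;
- deaths added: (1+1) to (2+3) = 2-5;
- complications sentence also applied: (1+1+2) to (2+3+6) = 4-11.

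**Step 3: what unblinded attribution could do.** Assume the same risk r of serious progression in both arms and 4% other serious events, with a fraction f of progression events set aside. The expected count per arm is 25 x [0.04 + r(1 - f)]. Take f = 0.9 in SOC and 0.6 in favipiravir:

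- r = 0.12: 25 x 0.052 = 1.3 v. 25 x 0.088 = 2.2
- r = 0.20: 25 x 0.060 = 1.5 v. 25 x 0.120 = 3.0
- r = 0.28: 25 x 0.068 = 1.7 v. 25 x 0.152 = 3.8

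With f = 0.9 in both arms and r = 0.20, the counts are 1.5 v. 1.5. Unequal labelling can therefore create a difference where none exists. The direction chosen here is arbitrary, and nothing in the documents shows that labelling would be unequal.

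**The case against.** The best defence is definitional order. Section 8.4.5 starts from the premise that an SAE is an AE, so 8.4.2 acts first and progression never reaches the seriousness test. The complications sentence closes a paragraph that explains what counts as a hospital admission, and it does not mention progression. This is a fair reading, but the text does not impose it. As written, the sentence covers every in-hospital complication, and the death line in the same section shows that 8.4.5 does override 8.4.2 at least once.

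A second defence is that keeping disease events out of AE reporting is a legitimate design choice when they are captured as outcomes. That stands, provided the rule is applied the same way everywhere.

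Two stronger readings are tempting, and neither is supported:

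- *A reader might infer that sites have no usable instruction for COVID-19 deaths.* They have one: 8.4.5 names the disease and requires an SAE. The gap is in the SAP's tabulation.
- *A reader might infer that a drug-related deterioration labelled as progression would vanish from the safety evidence.* It would not. All-cause mortality (SAP 4.3.2.7), the 6-point scale (4.3.2.1), respiratory progression (4.3.2.3.1) and oxygen or ventilation requirement (4.3.2.5) are compared by arm without AE attribution, and laboratory shifts are tabulated (4.5.3). What those analyses do not do is bring an individual event into causality or SUSAR review.

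**Conclusion.** The inconsistency is real and is in current text. For non-fatal serious progression, two sites that each follow the protocol may record the same event differently. For COVID-19 deaths, recording is reasonably clear, but their place in the serious-TEAE and fatal-TEAE rows is not. The consequence is limited to AE/SAE tables and SAE/SUSAR reporting; no efficacy analysis is affected.

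The size cannot be stated from the documents. The bound of 10-20 points per arm rests on an assumed mortality in a population that excludes subjects on a ventilator at entry. The range from 1-2 to 4-11 subjects per arm likewise rests on assumed risks. A reader might go further and infer biased attribution; the open-label design makes that possible, but it is not shown. The point is worth correcting because the repair is cheap and settles what the between-arm serious-event table means.

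**What to change.** 1. Reconcile protocol 8.4.2, 8.4.5 and 9.7 and SAP 4.5.2 into one rule with one wording for the COVID-19 exclusion.
2. Carry the death exception of 8.4.5 into SAP 4.5.2, and say whether COVID-19 deaths count in the serious-TEAE and fatal-TEAE rows.
3. State whether the complications sentence in 8.4.5 covers COVID-19 progression. Either answer can be defended; the sponsor should choose one.
4. Add an eCRF flag for recorded serious events attributed to COVID-19. Section 8.4.3 already lets underlying disease be given as the reason an event is unrelated, so cause can be recorded without dropping the event.
5. Present serious and fatal TEAEs by arm with and without flagged events. Treat the version with all recorded serious events and deaths as the between-arm comparison, because it depends less on unblinded attribution.

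The flag has a limit: the same unblinded investigator sets it, and it cannot recover events that the chosen rule keeps from being recorded at all.

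Cost: a protocol and SAP clarification, one eCRF field, one extra table and, depending on the rule chosen, possibly more SAE forms for sites.

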8.4.3 Evaluating and Reporting of Adverse Events

All AEs (i.e. a new event or an exacerbation of a pre-existing condition) that occur after dosing with favipiravir and after completion of baseline assessments in the SOC alone arm, must be recorded as an AE or SAE (if applicable), on the Adverse Event eCRF and SAE form, as applicable. The Investigator must follow all AEs until the AE resolves, or until the Investigator and/or the Medical Monitor determine the event is chronic or clinically stable. If an AE remains unresolved at the conclusion of the study, the Investigator and Medical Monitor will make a clinical assessment to determine whether continued follow-up of the AE is warranted. All subjects who have received at least one exposure to study therapy will be evaluated for safety of study treatment.

The Investigator should attempt to establish a diagnosis of the event based on signs, symptoms and/or other clinical information. In such cases, the diagnosis should be documented as the AE and not the individual signs/symptoms.

All AEs must be promptly documented on the Adverse Event eCRF and assessed by the Investigator. Details of the event must include the dates of onset and resolution, severity, relationship to study drug, seriousness, and whether the event caused the subject to withdraw from the study, outcome and timing with regard to administration of the study drug.

Severity: Severity should be graded and recorded as follows:

- Mild: Awareness of event but easily tolerated
- Moderate: Discomfort enough to cause interference with usual activity
- Severe: Inability to carry out usual activity, incapacitating, requires medical intervention

Relationship: The relationship of the Adverse Event to the study drug will be determined by the Principal Investigator, and assessed using the following definitions:

• **Related:** There is a distinct temporal relationship between the event onset and administration of the study drug. There is a known reaction to agent or chemical group or

predicted by known pharmacology. The event cannot be explained by subject's clinical state or other factors.

• Unrelated: Evidence exists that the AE has an etiology other than the study drug (e.g., pre-existing condition, underlying disease, intercurrent illness, or concomitant medication).

These criteria, in addition to good clinical judgment, should be used as a guide for determining the causal assessment. If it is felt that the event is not related to study drug therapy, then an alternative explanation should be provided.

8.4.4 Serious Adverse Events (SAEs)

All SAEs as defined below and that occur after the first dose of favipiravir and up to Day 60 (which is 46 days after the last planned study drug administration) must be reported to the Sponsor as soon as the site becomes aware of them. Any SAEs occurring after Day 60 (more than 46 days after last planned study drug administration) and considered at least possibly drug-related must also be reported.

8.4.5 Definition of Serious Adverse Events

An SAE is an AE from this study that results in any of the following outcomes:

- Death (even if caused by COVID-19 all deaths are recorded as SAEs)
- Life-threatening situation (subject is at immediate risk of death)
- Inpatient hospitalization or prolongation of existing hospitalization
- Persistent or significant disability/incapacity
- Congenital anomaly/birth defect in the offspring of a subject who received study drug

NOTE: Important medical events that may not result in death, be immediately life-threatening, or require hospitalization, may be considered an SAE when, based upon appropriate medical judgment, they may jeopardize the subject *and* may require medical or surgical intervention to prevent one of the outcomes listed in this definition.

A life-threatening AE is defined as any adverse experience that places the subject in the view of the Investigator, at immediate risk of death from the event as it occurred. This does not include an event that might have led to death, if it had occurred with greater severity.

"Inpatient hospitalization" means the subject has been formally admitted to a hospital for medical reasons, for any length of time. Presentation and care within an emergency department does not necessarily constitute an SAE. Complications that occur during hospitalization are AEs. If a complication prolongs hospitalization, it is an SAE.

8.4.6 SAE Reporting Requirements to the Sponsor

The procedure for reporting SAEs, regardless of causal relationship, is as follows:

- Within 24 hours of the Investigator's knowledge of an SAE, the site must notify the Sponsor by phone call to their site monitor, medical monitor or other Sponsor representative. They should also immediately complete the AE eCRF and select "Serious".
- This initial reporting of an SAE should contain as much information as is available to the Investigator. Submission of the SAE via the EDC should not be delayed in order to collect additional information to complete the form.
- Follow-up SAE reports may be generated in cases in which additional information becomes available. Hospital records, autopsy reports, and other documents may become available and scanned copies can be provided to the Sponsor when applicable. The follow-up SAE report should describe whether the event has resolved or continues, if and how it was treated, whether the blind was broken or not, and whether the subject continued or withdrew from study participation.
- The Sponsor will distribute completed SAE forms, which may be used to notify the IRB when applicable, via a secure internet-based document depository.
- The Investigator should notify the IRB of Serious Adverse Events occurring at the site and other adverse reports received from the Sponsor in accordance with local procedures.

The Investigator must take all therapeutic measures necessary for resolution of the SAE. Any medications necessary for treatment of the SAE must be recorded onto the concomitant medication section of the subject's eCRF.

8.5 Suspected Unexpected Serious Adverse Reactions (SUSARs)

A SUSAR carries specific and time-based reporting requirements for the Sponsor of a clinical trial. Thus, after an Investigator reports an SAE, the FDA expects the Sponsor will determine whether it meets the definition of a SUSAR.

A SUSAR is defined according to 3 criteria:

- 1. The AE is deemed a "suspected adverse reaction" if there is a reasonable possibility that the study drug caused the AE. A "reasonable possibility" means there is evidence to suggest a causal relationship between the drug and adverse event.
- 2. The AE is "Serious" if it meets the definition of an SAE provided in section 8.4.5
- 3. The AE is deemed "unexpected" if it is not listed in the Investigator's Brochure (IB) or if in the IB, has not been reported at the severity observed.

In cases where the Sponsor deems a SUSAR has occurred, it must file an IND Safety Report with the FDA. FPHU will require the assistance and cooperation of the Investigator and staff to provide accurate and complete information on the subject and observed SAE so that reporting requirements to the FDA can be met.

8.5.1 Reporting SUSARs to the FDA: IND Safety Reports

IND safety reports are used to submit reports of SUSARs to the FDA. There are 2 types of reports:

• A "15-day report" is used when the reported SAE is a SUSAR and requires that as much information as is available to the investigator and the sponsor, be submitted to the FDA in on

the appropriate form. For US trials, the appropriate form is the FDA Form 3500A also commonly known as a "MedWatch" form.

• A "7-day report" is used when the SUSAR is considered to be fatal or life-threatening.

The 7-day and 15-day timelines begin the day that the Investigator learns of the event and are counted in calendar days – not business days. Therefore, it is important that the investigator carefully follow the reporting requirements described in section 8.4.6.

